8.2.1. Use of Rescue Steroids

Triggering criteria:

A modification of the corticosteroid regimen is indicated if the following events occur in the trial:

1. A positive gamma interferon ELISPOT response to AAVrh8 capsid or HEXA/B transgene peptide pools on two successive ELISPOT assays done on or prior to the 3-month post-dosing time point. Please note that if one ELISPOT is positive, the assay should be repeated within 1 to 2 weeks.

AND EITHER

2. A worsening of clinical neurological signs or symptoms felt to be indicative of inflammation and/or injury, including but not limited to physical and neurological examination, CSF analysis and neuroimaging studies.

OR

3. An increase in ALT to $2\times$ the pre-dosing level or $3\times$ the upper limit of normal.

If these conditions are met the following regimen will be completed:

- 1. Methylprednisolone administered IV at 10 mg/kg/day for 3 successive days.
- 2. Followed by resumption of prednisolone at 2 mg/kg/day for at least 3 weeks prior to resumption of the scheduled weaning protocol.
- 3. Adjustment of sirolimus dose to achieve a trough level of 10-15 ng/mL for at least 3 weeks prior to resumption of dosing to achieve a level of 7-12 ng/mL, followed then by the scheduled plans for continuation and weaning.

If these conditions are not met, but the indicators ALT and ELISPOT are trending higher, the PI may, at his or her discretion increase the prednisolone dose within the range of 1 to 2

Confidential Page 42 of 97

AXO-AAV-GM2

UMass Chan Medical School Clinical Study Protocol: AXO-GM2-001

Version 8.0, 09 June 2023

mg/kg/day and/or increase the sirolimus dose to achieve a trough level at a higher than the prior baseline, but still within the reference range (i.e., still less than 18 ng/ml).

8.3. Study Justification

8.3.1. Study Design

The uncontrolled study design is based on the consideration that TSD and SD are rapidly progressing and predictably fatal conditions for which natural history data exist with well-defined outcome measures very similar to those included in this study (Bley et al. 2011, Utz et al. 2017) can be used as a non-concurrent comparative/control group to measure treatment effect of AXO-AAV-GM2.

TSD and SD pathophysiology is well understood, and the natural history data reflect concurrent management of the condition during the disease-course of these patients. The natural history data highlight the homogeneity of the infantile TSD and SD population and the consistent and predictable clinical course involving the attainment of early milestones followed by developmental regression within a short time span. These factors allow for results of this study to: 1) be clearly interpretable as the treatment effect is expected to exceed the known variability in progression, 2) is not affected by patient or investigator motivation or choice of participants for treatment, 3) be objectively measured in a manner that reasonably manages and minimizes bias, 4) have a strong temporal association with administration of the investigational drug, and 5) is consistent with expected pharmacological activity based on the target and animal models. As there is limited experience with stereotactic intracerebral infusions in infants, and to manage potential safety concerns associated with AAV gene therapy, the first participant dosed in the low, mid, and high dose groups of Stage 1 will be a juvenile-onset participant to facilitate the stepwise escalation of intra-thalamic infusion volumes and doses.

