- Dosing of subsequent participants will only occur after satisfactory DSMC and Sponsor review of 4-week safety data from the previously dosed participant as well as accumulated safety data from all previously dosed participants in the trial. In the Mid and High dose cohorts, after the DSMC has reviewed the 4-week safety data from the first (Juvenile) participant, an infantile and second Juvenile participant may be treated concurrently.

An additional participant may be entered at any dose level if a participant is lost to follow-up or experiences $a \ge Grade 3$ related AE before 4 weeks post-gene transfer. Each staggered participant may start limited screening activities, as detailed in the schedule of assessments for juveniles (Table 14) and infants (Table 15), respectively. The rest of the study assessments can be pursued only once the DSMC and Sponsor approve the dosing of additional participants.

Gene transfer will be administered over the course of two days (Section 11.5) as follows:

- At Visit 1a/Day 1, participants will receive bilateral intraparenchymal infusions of AXO-AAV-GM2 into the thalamus (BiTh)
- At Visit 1b/Day 2, participants will receive ICM/IT infusion of AXO-AAV-GM2 into the CSF

All AXO-AAV-GM2 infusions will be comprised of a 1:1 mixture of rAAVrh8-*HEXA* and rAAVrh8-*HEXB*.

To ensure venous access and ability to draw protocol specified safety labs, as well as reduce the pain associated with difficult blood draws during the study, a central venous catheter may be inserted with caregiver consent prior to surgical gene transfer.

Following gene transfer, Stage 1 juvenile participants will be assessed for safety and efficacy over a 2-year period, during which they will undergo safety, biomarker, neurocognitive, neurologic and motor function assessments according to Table 14. Stage 1 infantile participants will undergo safety, biomarker, neurologic and motor function assessments according to Table 15 over a 1-year period. Neurologic and motor function assessments may be videotaped.

Confidential Page 6 of 97

UMass Chan Medical School

Clinical Study Protocol: AXO-GM2-001

Version 8.0, 09 June 2023

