- At Visit 1a/Day 1, participants will receive bilateral intraparenchymal injections of AXO-AAV-GM2 into the thalamus (BiTh) at doses outlined in Table 1.
- At Visit 1b/Day 2, participants will receive ICM/IT infusion of AXO-AAV-GM2 into the CSF via microcatheter at doses outlined in Table 2.

Table 1: Stage 1 Bilateral Intrathalamic (BiTh) Doses – Visit 1a/Day 1

Group	Participant	Volume of Infusion (per thalamus)	Dose (per thalamus)	Intraparenchymal Catheter
Starting Dose	Participant (I or J)	0.18 mL	5.87E+12 vg	SmartFlow
	Participant (J)	0.36 mL	1.17E+13 vg	BrainLab Flexible
Low Dose	Participant (I)	0.36 mL	1.17E+13 vg	BrainLab Flexible
	Participant (J)	0.36 mL	1.17E+13 vg	BrainLab Flexible
	Participant (J)	0.72 mL	2.35E+13 vg	BrainLab Flexible
Cohort 1	Participant (I)	0.72 mL	2.35E+13 vg	BrainLab Flexible
(Mid-Dose)	Participant (I)	0.72 mL	2.35E+13 vg	BrainLab Flexible
Cohort 2	Participant (I)	1.25 mL	4.08E+13 vg	BrainLab Flexible
(High-Dose)	Participant (I)	1.25 mL	4.08E+13 vg	BrainLab Flexible

Note: Dosing based on final titer of 3.26E+13 vg/mL (1:1 mixture of AAVrh8-HEXA:AAVrh8-HEXB)

Table 2: Stage 1 ICM/IT Doses: Visit 1b/Day 2

Group	Participant	Total ICM/IT Infusion Volume	Dose
Starting Dose	Participant (I or J)	4.00 mL	1.30E+14 vg
	Participant (J)	5.25 mL	1.71E+14 vg
Low Dose	Participant (I)	5.25 mL	1.71E+14 vg
	Participant (J)	5.25 mL	1.71E+14 vg
	Participant (J)	5.25 mL	1.71E+14 vg
Cohort 1	Participant (I)	5.25 mL	1.71E+14 vg
(Mid-Dose)	Participant (I)	5.25 mL	1.71E+14 vg
Cohort 2	Participant (I)	8.40 mL	2.74E+14 vg
(High-Dose)	Participant (I)	8.40 mL	2.74E+14 vg

Note: Dosing based on final titer of 3.26E+13 vg/mL (1:1 mixture of AAVrh8-HEXA:AAVrh8-HEXB)

- 75% of the intended ICM/IT dose will be infused into the cisterna magna
- 25% of the intended ICM/IT dose will be infused at a thoracolumbar level (T12/L1)

The total dose (vg) of AXO-AAV-GM2 that will be administered during Stage 1 per participant ranges from 1.42E+14 to 3.56E+14 vg (Table 3).

Confidential Page 12 of 97

AXO-AAV-GM2

UMass Chan Medical School

Clinical Study Protocol: AXO-GM2-001

Version 8.0, 09 June 2023

Table 3: Total Vector Dose per Participant: BiTh and IT Dosing

Group	Participant	BiTh Dose	ICM/IT Dose	TOTAL DOSE
Starting Dose	Participant (I or J)	1.17E+13 vg	1.30E+14 vg	1.42E+14 vg
	Participant (J)	2.35E+13vg	1.71E+14 vg	1.95E+14 vg
Low Dose	Participant (I)	2.35E+13vg	1.71E+14 vg	1.95E+14 vg
	Participant (J)	2.35E+13vg	1.71E+14 vg	1.95E+14 vg

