8.1.1.1. Stage 1 – Dose Escalation

Stage 1 dosing consists of a Starting Dose, Low Dose, Mid Dose, and High Dose (Figure 6). The first participant enrolled in the study can be either sub-type (infantile or juvenile) and will be administered the Starting Dose. Prior to dosing of each participant, the independent DSMC must review the available safety data from all previous participants and make a recommendation regarding continued enrollment and dose escalation. Additional participants beyond those planned in a cohort may be dosed, for example, if requested by the DSMC or regulatory agency, or if a participant within a dose level cohort is lost to follow up or experiences a ≥ Grade 3 related AE before 4 weeks post-gene transfer.

Requirements for dose escalation or progression to Stage 2 of the study are as follows:

1. DSMC recommendation to continue as planned, and:

Confidential Page 38 of 97

[figure not shown]
Clinical Study Protocol: AXO-GM2-001

Version 8.0, 09 June 2023

• At the Low Dose: at least 4 weeks of safety data are available from 2 juvenile and 1 infantile participant administered the Low Dose.

- For the Mid Dose and High Dose:
 - At least 4 weeks of safety data from at least 1 juvenile participant and 2 infantile participants are required to dose escalate.
 - In addition, dose escalation of juvenile participants may also occur based on at least 4
 weeks of safety data from at least 2 juvenile participants and may occur prior to infantile
 dose escalation.

Figure 6: Stage 1 Dose Escalation Scheme

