(Mid Dose)	Participant (I)	4 μL/min	2.35E+13 vg	720	bilaterally)		Operating Room †
	Participant (I)	4 μL/min	2.35E+13 vg	720			Operating Room †
Cohort 2	Participant (I)	4 μL/min	4.08E+13 vg	1,250	312 min (5.2 hours)		Operating Room †† or PICU*
(High Dose)	Participant (I)	4 μL/min	4.08E+13 vg	1,250	(simultaneous bilaterally)		Operating Room †† or PICU*

OR = Operating Room

Confidential Page 49 of 94

[†] Limited intra-operative CT scan of the brain will be performed shortly after bilateral infusion catheter placement and mid-way through the infusion. At the discretion of the surgeon, infusions will be stopped if there is evidence of bleeding or injury, or an emergent adverse event

^{††} For infusions within the OR, additional intra-operative CT scans of the brain may be performed

^{*} PICU infusion is at the discretion of neurosurgeon and based on safety results of prior treated participants' outcomes. If the surgeon elects to perform the infusion within the PICU, a single limited intra-operative CT scan of the brain will be performed shortly after bilateral infusion catheter placement and the participant will then be transferred

Clinical Study Protocol: AXO-GM2-001

Version 8.0, 09 June 2023

To achieve the broadest distribution of vector and transgene expression, the goal of the BiTh infusion is to fill as much of the thalamus as possible using a dosing scheme that holds the vector concentration constant (based on a titer of 3.26E+13~vg/mL) and to progressively increase the volume of infusion across consecutive participants. As infusion volume increases, so does the total vector dose (these dosing parameters are inherently confounded). The amount or % of the target thalamus that is filled with vector is based on the use of convection enhanced delivery (CED) to drive AAV through the brain parenchyma using pressure (Bobo et al. 1994). Infusion rates between 1 and 5 μ L/min are typically used with CED and this technique has been successfully applied across many nonclinical and clinical studies to increase the distribution of a wide range of therapeutic agents including AAV (Ellinwood et al. 2011, Tardieu et al. 2017, Chien et al. 2017, Christine et al. 2019, Hudry et al. 2019, Kells et al. 2009, Yin et al. 2010). For delivery of AXO-AAV-GM2, an infusion rate of 4 μ L/min will be used across all participants for CED of the vector. As shown in Table 11, the time for bilateral infusion will range from 1.5 to 5.2 hours.

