8.6. Dose Adjustment Criteria

Stage 1 dose escalation is defined in Section 8.3.4. Stage 2 dose will be based on results of Stage 1. Following selection of dose for Stage 2, no dose adjustments will be allowed.

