17. STUDY COMMITTEES

17.1. Independent Data and Safety Monitoring Committee (DSMC)

The DSMC is an independent multidisciplinary group (independent of both the sponsor and CRO) who collectively has experience in the management of participating participants as well as in the conduct and monitoring of clinical trials.

The DSMC will meet at regular intervals allowing for the timely review of 4-week safety data for Stage 1 participants (see Section 8.1.1). The DSMC and Sponsor will determine whether enrollment of participants may proceed according to the dose-escalation plan (Table 10). Based on satisfactory review of 4-week safety data for each participant, accrued safety data of all participants, and review for potential safety signals related to AXO-AAV-GM2 as well as that of the neurosurgical administration/infusion procedures, the DSMC may recommend to continue the study as designed, to continue the study with modifications (e.g. dose descalation/escalation in the event of toxicity), or to terminate the study early based on the safety.

After the last Stage 1 participant has been dosed and observed for 4 weeks, the DSMC will review the cumulative safety data in conjunction with the Sponsor and determine the optimal AXO-AAV-GM2 dose regimen to be administered in Stage 2. The DSMC will continue to meet at regular intervals throughout the duration of the study.

The DSMC will review enrollment progress, baseline characteristics of the study population, all treatment-emergent safety reports, clinical laboratory and imaging data. The members of the DSMC will be notified of all SAEs.

Additional details regarding the specifics of the DSMC operations may be found in the DSMC Charter.

Confidential Page 89 of 97

Version 8.0, 09 June 2023

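### The text doses a juvenile first at the High Dose, but all nine dose tables, including the one the DSMC is told to use, list only two infants there and 9 of the 12 Stage 1 participants

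*Combined protocol and SAP*

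**What the plan says.** **The narrative.** Section 8.3.1 commits to a juvenile first at three dose levels: "the first participant dosed in the low, mid, and high dose groups of Stage 1 will be a juvenile-onset participant". Its reason is that little is known about stereotactic infusion into the infant brain. The synopsis is consistent: at Mid and High, once the DSMC has reviewed the first juvenile's 4-week data, "an infantile and second Juvenile participant may be treated concurrently". Section 8.1.1.1 opens its rule with "Requirements for dose escalation or progression to Stage 2 of the study are as follows" and, for the Mid and High Doses, says "At least 4 weeks of safety data from at least 1 juvenile participant and 2 infantile participants are required to dose escalate". A further bullet lets juveniles escalate ahead of infants on data from at least two juveniles.

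**The tables.** Tables 1, 2, 3, 8, 9, 10, 11, 12 and 13 all give the same participants: Starting Dose one (I or J); Low J, I, J; Mid J, I, I; High I, I. In Table 1, for example, both High Dose rows are infants, the first reading "Cohort 2 Participant (I) 1.25 mL 4.08E+13 vg BrainLab Flexible".

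**Which one governs.** Section 8.6 says "Stage 1 dose escalation is defined in Section 8.3.4", the section that holds Tables 10-13. Section 17.1 says "The DSMC and Sponsor will determine whether enrollment of participants may proceed according to the dose-escalation plan (Table 10".

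**The count.** The synopsis and Sections 8.1, 8.4 and 14.2 all plan 12 participants in Stage 1. Section 14.1 speaks of one or two participants per dose.

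**The concern.** The treatment is given once and, as Section 9.3 notes, cannot be withdrawn, so the order of dosing is itself a safety measure. The protocol states that measure in the text and leaves it out of the tables that the DSMC and sponsor are told to use. A site working from Table 10 would give the High Dose to an infant with no juvenile treated at that level beforehand. That is the situation Section 8.3.1 is meant to avoid, at the level with the thinnest margins.

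The tabulated High Dose cohort (no juveniles, two infants) also fails the stated data requirement of one juvenile and two infants. The protocol does not say plainly whether that requirement controls entry to Stage 2.

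**Working it through.** **1. Count the participants.** Rows per table, Starting + Low + Mid + High:

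- Tabulated: 1 + 3 + 3 + 2 = 9, against 12 planned. Three are missing.
- High Dose juveniles tabulated: 0, against at least 1 in the text.
- Adding only the leading High Dose juvenile: 1 + 3 + 3 + 3 = 10, still not 12.
- Two juveniles and two infants at both Mid and High, as the synopsis wording allows: 1 + 3 + 4 + 4 = 12, which matches. On this reading the tables lack one juvenile at Mid and two at High.

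**2. Reproduce the plan's High Dose figures for infants.** Margin = scaled volume (Tables 6 and 7) / planned volume. Fill = 3 x infusion volume / thalamic volume (Table 11).

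- Thalamic margin: 1.10 / 1.25 = 0.88 (stated 0.9).
- ICM/IT margin: 6.92 / 8.40 = 0.82 (stated 0.8).
- Fill: 3 x 1,250 / 4,322 = 86.8% (stated 87%).

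**3. Apply the same formulas to a High Dose juvenile.** Sections 8.3.3.4 and 8.3.4.1 give juvenile values for Cohort 2 and cite Tables 9 and 11, neither of which has such a row.

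- ICM/IT margin: 7.86 / 8.40 = 0.94 (text: 0.9).
- Fill: 3 x 1,250 / 4,990 = 75.2% (text: 75%).
- Thalamic margin: 1.28 / 1.25 = 1.02 (text: at least 1.0 for all except High Dose infants).

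The text figures match a juvenile treated at the High Dose volumes. The narrative was therefore written for a participant whom the tables omit.

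**4. Size of the step at the High Dose.**

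| Step | Total dose (vg) | Ratio | Volume per thalamus (mL) | Ratio | ICM/IT volume (mL) | Ratio |
|---|---|---|---|---|---|---|
| Starting to Low | 1.42E+14 to 1.95E+14 | 1.37 | 0.18 to 0.36 | 2.00 | 4.00 to 5.25 | 1.31 |
| Low to Mid | 1.95E+14 to 2.18E+14 | 1.12 | 0.36 to 0.72 | 2.00 | 5.25 to 5.25 | 1.00 |
| Mid to High | 2.18E+14 to 3.56E+14 | 1.63 | 0.72 to 1.25 | 1.74 | 5.25 to 8.40 | 1.60 |

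The Mid to High step adds 3.56E+14 - 2.18E+14 = 1.38E+14 vg. It is the largest of the three in total dose and in ICM/IT volume. For the thalamus it is the smallest ratio but the largest absolute increase: 0.53 mL, against 0.18 and 0.36 mL.

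**5. Compare the Mid cohort with the early-escalation bullet.** The route by which juveniles move up first needs data from two juveniles. The Mid cohort as tabulated has one, so that route from Mid is not available without an untabulated participant.

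**The case against.** The strongest reply is that this is incomplete table editing, not a rival safety plan. The narrative statements all point the same way, and no table says that its rows are in time order. Section 17.1 also refers the DSMC to Section 8.1.1, which contains the juvenile data requirement, and leaves operating details to a charter that is not among the documents. Figures 1 and 6, which set out the escalation scheme, are not shown and may list all 12. Section 8.1.1.1 requires DSMC review before every dosing, and Section 9.4 suspends dosing for related serious events. The sub-1 margins are openly disclosed.

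Much of this is fair as to cause, but it does not remove the conflict. Row order does not matter when no High Dose juvenile is listed at all. DSMC review is a real safeguard but does not itself impose juvenile-first, and the plan it is told to apply is Table 10. Figures that list 12 would still disagree with nine tables. The allowance for extra participants covers those beyond the planned number, and 12 is the planned number.

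Three qualifications stand:

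- The thalamic ratio at High is the smallest of the three.
- The data requirement is worded for escalation and reaches Stage 2 only through its heading, while Section 8.1.1 describes the Stage 2 decision separately. However, no Stage 1 dose lies above High, so its High Dose limb has no other use.
- The Section 14.1 wording could be read per subtype, but that reading is stated nowhere, and Low and Mid have three rows each.

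**Conclusion.** The concern holds and must be fixed. The protocol puts a juvenile first at the High Dose in its text and lists none there in any dose table: 0 against at least 1, and 9 participants against 12. A PDF fault is unlikely, because nine tables in different layouts agree. If Table 10 is followed, an infant is dosed first at the only level with stated infant margins below 1, against the protocol's own safety reasoning.

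This is an unresolved inconsistency, not a requirement that can never be met, since participants may be added and the DSMC reviews each dosing. The 1 + 3 + 4 + 4 breakdown is an inference, because the synopsis only permits the second juvenile to be treated alongside the infant. The documents do not say how many participants had been treated by this version.

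**What to change.** - Add the High Dose juvenile, marked as dosed first, to Tables 1-3 and 8-13.
- Reconcile the rows with 12 and state the breakdown by dose and subtype. If two juveniles and two infants at both Mid and High is the intent, say so.
- Correct the per-dose sample size in Section 14.1.
- State explicitly that data from one juvenile and two infants are required to move from the High Dose to Stage 2.
- If infants only are intended at High, amend Section 8.3.1, the synopsis, the data requirement in Section 8.1.1.1, the juvenile High Dose figures in Sections 8.3.3.4 and 8.3.4.1, and the total of 12. Give a documented safety justification and obtain DSMC agreement before any infant receives that dose. If one has already been treated, document the actual order.

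The cost is amendment wording and DSMC confirmation. Up to three added rows stay within the planned 12, and no new procedure is needed.

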8.3.2. Immune Tolerance Induction (ITI) Regimen Justification

The prophylactic ITI regimen will be administered starting 7 days prior to gene transfer and will continue to week 24 to prevent antibody response to AAV capsid in participants receiving gene therapy. The potential for immune modulation to prevent antibody response to AAV capsid in participants receiving gene therapy was demonstrated by Corti et. al following a trial of intra-diaphragmatic injection of AAV1-GAA in participants with infantile Pompe disease (Corti et al. 2017). Three CRIM negative participants receiving AAV1-hGAA had also received chronic immune modulation with rituximab and sirolimus due to pre-existing immune responses to enzyme replacement therapy (ERT). These participants had no immunologic response to AAV capsid proteins or the GAA protein. This was in contrast to the 5 CRIM positive participants who had not received immune modulation and had an average 150-fold increase in anti-AAV1 titer after exposure to AAV1.

Immune modulation using rituximab has become the therapy of choice for CRIM negative infants to maintain the efficacy of ERT (Elder 2013, Kazi 2017).

A similar mitigation of antibody response to AAV9 capsid and therapeutic protein has been observed in an expanded access trial of intravenous plus ICV administration of rAAV9-hASPA

Confidential Page 43 of 97

UMass Chan Medical School Clinical Study Protocol: AXO-GM2-001

Version 8.0, 09 June 2023

transgene in a child with Canavan disease (Corti et al. 2018). In this study with rituximab and sirolimus preconditioning, the immune response was abrogated.

In another ongoing trial, "Re-administration of Intramuscular AAV9 in Subjects with Late-Onset Pompe Disease," (NCT02240407, IND #17404) a similar immune modulation strategy to ablate B- and T-cells (rituximab, sirolimus, methylprednisolone and prednisone) prior to the initial exposure to AAV9 by intramuscular injection prevented the formation of antibody against AAV9 and the GAA transgene.

The ITI regimen was administered and well-tolerated in the two TSD subjects that are part of an ongoing Expanded Access clinical trial for AAVrh8-*HEXA/HEXB* gene therapy (IND# 18225).

